#### 2.15.4 Analysis of Demographic and Medical History Variables

Summaries will be prepared for all important demographic and medical history variables. For quantitative variables summaries will include the sample size, mean, median, standard deviation, minimum, and maximum. For these variables the treatment groups will be compared using either a t-test or a Wilcoxon Rank Sum test, as appropriate. For categorical variables the summaries will include the sample size and the number and percent of patients for each outcome. For these variables the treatment groups will be compared using Fisher's Exact test. Statistical significance will be declared if the two-sided p-value is  $< 0.05$ .

#### 2.15.5 Analysis of Efficacy Variables

Additional efficacy variable is the change from baseline to Visit 11 (90 day follow up visit). Baseline is defined as the last assessment prior to the first treatment. The change from baseline to visits 10 and 11 will be analyzed using a Mixed Model Repeated Measures Analysis of Variance. A pairwise treatment group comparison at visit 11 will be performed using the results of this analysis. If a patient has no post-baseline assessment of the primary efficacy variable it will be assumed that the change from baseline to visit 11 is zero. The changes to visits 10 and 11 will be left as missing. Statistical significance with respect to the treatment group comparison at visit 11 will be declared if the two-sided p-value is  $< 0.05$ . For each treatment group, summaries will be prepared for both the observed assessment and the change from baseline. The summaries will include the sample size, mean, median, standard deviation, minimum, and maximum. The statistical significance of the mean change from baseline for each treatment group will be determined using a paired t-test.

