## 2.0 PROTOCOL

### **2.1 Protocol Methodology and Analysis**

Methodology:

Subjects are to be enrolled in this clinical study if they are a healthy male or female 18 years of age or older. Up to 30 subjects will be enrolled at 1 study center. Subjects will be enrolled into 2

groups, Group A and Group B. Subjects will be enrolled in Group A if they present with abdominal fat and are able to be present for all visits as outlined in “Schedule of Visits and Procedures – Group A”. Subjects will enroll in Group B for training and experience purposes only and will follow the visit schedule as outlined in “Schedule of Visits and Procedures – Group B”. Randomization will not be required as each subject will be assigned to a group depending on the purpose of their treatment(s). All subjects will attend a screening/pretreatment visit which may be performed on the same day as the treatment visit.

Subjects in Group A will receive up to 8 treatments with the Brera/Med 400 device on their abdomen or flanks. Subjects may receive a phone call 1 week (1-7 days) after each treatment to record side effects. Subjects will return for follow up visits at 30 and 90 days post last treatment for efficacy and side effects assessments.

Subjects in Group B may receive up to 8 treatments with the Brera/Med 400 device on their abdomen and/or flanks. Subjects may receive a phone call 1 week (1-7 days) after each treatment to record side effects. Subjects may be asked return for follow up visits at 30 and 90 days post last treatment for efficacy and side effects assessments.

An unscheduled visit or phone call may be performed at any time during the study at the request of the subject or as deemed necessary by the site Investigator.

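### The only efficacy test in 2.15.5 with a stated p<0.05 rule compares Groups A and B, which are not randomized and receive the same device, so it cannot inform device efficacy

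*Combined protocol and SAP*

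**What the plan says.** Section 2.15.5 analyses change from baseline to visits 10 and 11 with a repeated-measures mixed model and then states: "A pairwise treatment group comparison at visit 11 will be performed using the results of this analysis". The decision rule follows: "Statistical significance with respect to the treatment group comparison at visit 11 will be declared if the two-sided p-value is" below 0.05. The same section plans by-group summaries and a within-group test: "The statistical significance of the mean change from baseline for each treatment group will be determined using a paired t-test". No threshold or confidence interval is attached to that test.

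Section 2.15.5 does not name the groups, but section 2.1 has only two. Subjects are assigned according to the purpose of their treatment, and randomization is expressly not required. "Subjects in Group A will receive up to 8 treatments with the Brera/Med 400 device", and Group B may receive up to the same number with the same device. Group A subjects must present with abdominal fat; no such condition is stated for Group B. "Subjects will enroll in Group B for training and experience purposes only". Section 2.2 describes an open-label, single-center study, and no sham or untreated arm appears anywhere.

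Section 2.15.3 nevertheless restricts the efficacy analysis to patients who are randomized and receive at least one treatment.

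**The concern.** A between-group test informs efficacy only if the groups differ in exposure to the device. Here both are exposed, so an effect they share disappears from the difference. A significant A-versus-B result would point to something else:

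- **Selection.** Groups are formed by purpose, and only Group A has the abdominal-fat condition.
- **Spacing.** Section 2.12 sets treatments 1 week apart ± 4 days in Group A and at least 3 days apart in Group B.
- **Treated area or number of treatments.** Section 2.1 allows abdomen or flanks in Group A and abdomen and/or flanks in Group B. The number is only capped, at 8 in each.
- **Selective return or measurement.** Group B's visits 10 and 11 are optional (2.8 Follow Up, 2.12). So are its circumference, ultrasound and strength measurements, even at baseline (2.6, 2.12). Some Group A measures are also worded as optional (2.8 Follow Up, 2.12, 2.13), but Group A's follow-up visits are not.

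Two misreadings are likely. A null result may be taken as device failure, and a positive one as evidence that the device works. Meanwhile the Group A change from baseline, which does bear on fat and muscle change, has no stated decision rule. Read literally, the efficacy population in 2.15.3 contains nobody.

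**Working it through.** **Inputs.** From the documents: two groups, same device, no randomization (2.1); two-sided 0.05 (2.15.5); a total of 20 (2.15.2) or up to 30 (2.1). The documents give no split, SD, effect size or return rate, and no power figure for this comparison, so there is no planned figure to reproduce. Assumed: A/B = 20/10, 15/15 or 10/10, with change scaled so that its SD is 1.

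**Step 1: what each test estimates.** Write the mean change in group g as δ_g + b_g, where δ is the device effect and b is everything else.

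- A minus B estimates (δ_A − δ_B) + (b_A − b_B). If δ_A = δ_B, the device term is zero whatever its size. If spacing makes them differ, the term compares schedules, not device with no device.
- The Group A paired test estimates δ_A + b_A.

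**Step 2: response to a real change.** A two-sample t-test stands in for the visit 11 contrast, with the same true change in both groups and everyone attending. At changes of 0, 0.5, 1.0 and 1.5 SD it rejects 4.8% to 5.2% of the time (40,000 runs each). A two-visit mixed model at 1 SD gives 4.7% to 5.4% (2,500 runs).

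Group A paired t-test: power from the noncentral t with noncentrality d√n and n − 1 df; 95% CI half-width = t(0.975, n − 1)/√n.

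| Group A n | Power, d = 0.5 | Power, d = 1.0 | Half-width (SD) |
|---|---|---|---|
| 20 | 56.5% | 98.9% | 2.093/4.472 = 0.468 |
| 15 | 43.8% | 94.9% | 2.145/3.873 = 0.554 |
| 10 | 29.3% | 80.3% | 2.262/3.162 = 0.715 |

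**Step 3: rejection for reasons other than the device.** A-versus-B two-sample test:

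| Assumed scenario | 20/10 | 15/15 | 10/10 |
|---|---|---|---|
| Equal true change; only the better half of B returns (8 of 15 when n = 15) | 30.4% | 40.8% | 28.0% |
| Equal true change; 80% of better and 30% of worse responders in B return | 10.2% | 13.1% | 10.0% |
| Ineffective device; non-device difference of 0.5 SD | 23.6% | 26.2% | 18.2% |
| Ineffective device; non-device difference of 1.0 SD | 71.0% | 75.8% | 56.5% |

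**Step 4: does the mixed model rescue it?** Assumptions: REML, unstructured covariance, df = subjects with visit 11 minus 2, visit correlation 0.5 or 0.8, true change 1 SD, 2,500 runs.

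- Non-returners miss both visits: 26.5% to 41.2% for the better-half pattern and 9.3% to 12.7% for 80%/30%.
- Non-returners attend visit 10 and miss only visit 11: 11.0% to 29.4% and 5.6% to 11.0%. The inflation is smaller but mostly still present.

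**Step 5: the missing-data sentences.** For a patient with no post-baseline assessment, 2.15.5 says "it will be assumed that the change from baseline to visit 11 is zero" and then "The changes to visits 10 and 11 will be left as missing". Suppose a random half of Group B (7 of 15 when n = 15) has no post-baseline data and the true change is 1 SD. The zero rule gives 23.7%, 25.6% and 20.2% rejection; leaving the values missing gives 4.8%, 5.0% and 4.9%. That conflict is a separate point, but it shows how little the contrast depends on the device.

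**The case against.** The strongest reply is that little depends on this test. Efficacy is listed under optional assessments in 1.2. No success criterion in 2.15.1 uses A versus B: they are photograph identification of at least 80%, GAIS against a no-change score of 4, questionnaires collected, and acceptable side effects and pain. The within-group paired test is already planned, and 0.05 is the only level used in 2.15, so a reader could infer it. Section 2.15.3 limits its optional per-protocol analysis to Group A, which suggests that Group A was already seen as the cohort of interest and that the reference to randomization is leftover wording. The differing schedules also give the contrast some content.

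Most of this stands as a limit on consequence. The primary safety conclusion is untouched, and the GAIS and photograph assessments bear on appearance independently of this test. But the significance rule is still attached to the wrong comparison. A threshold for the informative test should be stated, not inferred. No objective in 1.2 asks about schedule, and any schedule effect is confounded with non-random assignment and optional attendance. The return scenarios are indeed assumptions; the structural argument in step 1 of the working does not need them.

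**Conclusion.** The concern holds. The one efficacy comparison for which 2.15.5 states a significance rule does not respond to an effect shared by both groups: rejection stays at about 5% for any common change from 0 to 1.5 SD. It can also reject for reasons unrelated to efficacy, in roughly 10% to 41% of trials under the assumed return patterns when non-returners miss both follow-up visits, and less when they miss only visit 11. The Group A paired test does respond, with 80% to 99% power at 1 SD and 29% to 57% at 0.5 SD for Group A sizes of 10 to 20.

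The 5% result assumes equal device effects in the two groups; the other figures rest on assumed splits, return patterns and, for the mixed model, visit correlations. The defect itself follows from the design alone. It should be fixed before the data are analysed, but it is confined to the optional efficacy assessments.

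**What to change.** 1. In 2.15.5, delete the A-versus-B comparison and its p<0.05 rule, or label the comparison descriptive.
2. Attach the rule to the analysis already planned, for example: *In Group A, the mean change between baseline and visit 11 will be tested against zero by a two-sided paired t-test at the 5% level and presented with its 95% confidence interval.*
3. In 2.15.3, remove the reference to randomization. Define the efficacy set as Group A subjects with at least one treatment. Summarize demographics and medical history by group for everyone with at least one treatment. Report Group B efficacy data descriptively and keep Group B in the safety set.
4. State that, without a control, change from baseline cannot be attributed to the device alone.

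Three gaps already in the plan remain and are best settled in the same amendment: which variable the test applies to (circumference, ultrasound and strength are all candidates), what role the mixed model keeps, and which missing-data sentence governs.

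**Cost.** A protocol amendment with written IRB approval (section 21.0), because the analysis plan sits inside the protocol. No added subjects, visits or measurements. The sponsor gives up a between-group p-value that does not inform device efficacy.

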#### Group A:

- Photographs will be taken prior to the 1st and 5th treatment, and may be taken prior to each subsequent treatment.
- Prior to treatment 1 and 5 only, circumference measurements and abdomen strength measurement will be taken, and ultrasounds may be performed.
- Prior to treatment 5 only, subjects will be asked to complete a Subject Treatment Questionnaire.
- For treatment 5 only, pre-treatment procedures and treatment may be separated into 2 visits.

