#### Group B:

- Photographs will be taken prior to their first treatment and may be taken prior to each subsequent treatment.
- Circumference measurements and abdomen strength measurements may be taken, and ultrasounds may be performed at any treatment visit.
- Subjects may be asked to complete a Subject Treatment Questionnaire prior to any treatment visit.

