### **2.8 Follow Up**

#### Group A:

- Subjects may receive a phone call 1 week (1-7 days) after each treatment to record side effects.
- Subjects will return for follow up visits at 30 and 90 days post last treatment.
- Photographs will be taken, adverse events will be documented, and subjects will be asked to complete questionnaires, objective measurements will be taken, and ultrasounds may be performed.
- Any subject affected by COVID-19 that is not able to attend their follow up visits to complete the study will be asked to return to the site for a final follow up visit within 1 year of last treatment.

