#### Group B:

- Subjects may receive a phone call 1 week (1-7 days) after each treatment to record side effects.
- Subjects may return for follow up visits at 30 and 90 days post last treatment.
- Photographs will be taken, adverse events will be documented, and subjects may be asked to complete questionnaires and objective measurements may be taken and ultrasounds may be performed.

Some subjects may have an incomplete response or no response by the end of the study. At the end of the study, treatments using an FDA approved/cleared treatment method may be discussed with the subject and obtained at the cost of the subject.

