#### 2.15.3 Patient Populations

Interim results may be collected and reported. All data will be analyzed at the end of the study. The primary analysis will be performed by the intention-to-treat approach. Everyone who begins the treatment is part of the study whether he or she completes the study or not. Additional per-protocol analysis may also be performed on subjects assigned to Group A who complete the entire clinical trial according to the protocol. The most appropriate method of handling missing values will be chosen based on the individual trial goals, endpoints and context.

The analysis of demographic, medical history, and efficacy variables will be based on all patients who are randomized and receive at least one treatment. The analysis of safety data will be based on all patients who receive at least one treatment, and have at least some safety data.

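### Section 2.15.5 makes the visit 11 change of a patient with no post-baseline data both zero and missing, and never names the variable that triggers the rule

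*Combined protocol and SAP*

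**What the plan says.** Section 2.15.5 analyses change from baseline to visits 10 and 11 with a mixed model for repeated measures, compares the treatment groups at visit 11 at two-sided 0.05, and tests each group's mean change with a paired t-test. Its missing-data rule opens with a condition, "If a patient has no post-baseline assessment of the primary efficacy variable", and says that it will then be "assumed that the change from baseline to visit 11 is zero. The changes to visits 10 and 11 will be left as missing".

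Section 2.15.3 adds a general statement: "The most appropriate method of handling missing values will be chosen based on the individual trial goals, endpoints and context". It also defines the intention-to-treat principle: "Everyone who begins the treatment is part of the study whether he or she completes the study or not".

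Whether a patient can meet the condition depends on what is measured after baseline:

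- **Group A, section 2.6:** "Prior to treatment 1 and 5 only, circumference measurements and abdomen strength measurement will be taken, and ultrasounds may be performed".
- **Group A, Follow Up section:** "Subjects will return for follow up visits at 30 and 90 days post last treatment".
- **Group B, section 2.6:** "Circumference measurements and abdomen strength measurements may be taken, and ultrasounds may be performed at any treatment visit".
- **Group B, Follow Up section:** "Subjects may return for follow up visits at 30 and 90 days post last treatment".

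**The concern.** The second sentence of the rule names visit 11 and carries no condition of its own. As written, one patient's visit 11 change is therefore both zero and missing. The visit 11 group means, the paired t-tests and the between-group p-value all depend on which sentence the analyst follows.

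The trigger is also undefined. Section 1.2 makes adverse events the primary objective and puts every efficacy measure among the optional assessments. Section 2.15.5 itself speaks only of an additional efficacy variable and names no instrument. A subject may have a later circumference but no later ultrasound, so the analyst cannot tell who falls under the rule.

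The study is open label and section 2.15.3 allows interim results to be reported. The choice between the two rules could therefore be made after results are known.

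**Working it through.** **1. Does another passage settle it?** No. Section 2.15.3 defers the missing-data method. No section assigns the zero rule and the missing rule to different patients or different analyses, and none names a primary efficacy variable.

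**2. Can the condition occur?** Yes, in either group.

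- *Group B:* circumference, strength and ultrasound are optional at every visit, and both follow-up visits are optional (sections 2.6 and 2.12, and Follow Up).
- *Group A:* follow-up is required and circumference is due before treatment 5. However, subjects may withdraw, after which no data are collected (section 12.0). Ultrasound is discretionary, strength is marked optional in the section 2.12 schedule, and section 2.13 makes circumference discretionary too.
- *No baseline:* Group B baseline measurements are optional as well. A subject without one has no change to set to zero on the ordinary reading, but the plan does not say so.

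The share of such patients in each group cannot be computed from the documents.

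**3. Bias under the zero rule.** Let both groups truly change by mu, and let shares fA and fB be set to zero independently of outcome. The expected means are mu(1 - fA) and mu(1 - fB), so A minus B is

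mu(1 - fA) - mu(1 - fB) = mu(fB - fA).

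The true difference is 0. With mu = -2 cm:

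- fA = 0, fB = 20%: -2 × 0.2 = -0.4 cm
- fA = 0, fB = 50%: -2 × 0.5 = -1.0 cm
- fA = 20%, fB = 50%: -2 × 0.3 = -0.6 cm
- fA = 20%, fB = 0: -2 × (-0.2) = +0.4 cm

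The bias is zero if mu = 0 or the shares are equal.

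**4. False-positive rate.** The plan gives a total of 20 (section 2.15.2) or up to 30 (sections 2.1 and 3.3). It gives no split, SD, effect or missing share, so all of those are assumptions. The simulation used normal changes with SD 2 cm, equal true change in both groups, a pooled t-test at two-sided 0.05, and 400,000 trials per tabulated cell.

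| Split A/B | True change | fA | fB 20% | fB 50% | fB 80% |
|---|---|---|---|---|---|
| 20/10 | -2 cm | 0 | 8% | 27% | 64% |
| 20/10 | -2 cm | 20% | 5% | 12% | 41% |
| 20/10 | -1 cm | 0 | 5% | 9% | 18% |
| 20/10 | -1 cm | 20% | 5% | 6% | 11% |
| 15/15 | -2 cm | 0 | 9% | 31% | 72% |
| 15/15 | -2 cm | 20% | 5% | 15% | 51% |
| 15/5 | -2 cm | 0 | 7% | 16% | 36% |
| 15/5 | -2 cm | 20% | 5% | 7% | 18% |
| 15/5 | -1 cm | 0 | 5% | 5% | 7% |
| 15/5 | -1 cm | 20% | 5% | 4% | 4% |

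- At fB = 10%, fA = 0 and -2 cm, the rate is 5% to 6% in all three splits.
- At -0.5 cm with a 20/10 split, it is 5% or lower for the shares in the table.
- In the reverse case (20/10, -2 cm, fA = 20%, fB = 0), it is about 9%.

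**5. Same question in a mixed model.** This check used REML, group-by-visit means, unstructured covariance, an assumed correlation of 0.7 between visits, a 20/10 split, -2 cm, and 20% of Group B with visit 10 but not visit 11.

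| Rule | fA | fB | False-positive rate | Mean A minus B | Trials |
|---|---|---|---|---|---|
| Zero | 0 | 20% | 8.7% | -0.44 cm | 1,500 |
| Zero | 0 | 50% | 32.6% | -1.17 cm | 1,498 |
| Zero | 20% | 50% | 14.6% | -0.76 cm | 1,996 |
| Zero | 20% | 20% | 5.7% | about 0 | 1,500 |
| Missing | 0 | 50% | 4.7% | +0.06 cm | 527 |
| Missing | 20% | 50% | 5.4% | +0.09 cm | 519 |

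With partial data of this kind and unequal shares, the zero-rule bias is somewhat larger than mu(fB - fA). The rows for the missing rule assume data missing completely at random, and their differences are within simulation error.

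**6. Within one group.** Take 16 observed changes with mean -2 and SD 2, and 4 subjects without data.

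- *Left missing:* mean -2.0, SE = 2/√16 = 0.50, absolute t = 4.00.
- *Set to zero:* mean = (16 × -2)/20 = -1.6. Sum of squares = 15 × 4 + 16 × 0.4² + 4 × 1.6² = 72.8. SD = √(72.8/19) = 1.957, SE = 1.957/√20 = 0.44, absolute t = 3.66.

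The estimate falls by a fifth, while the test statistic moves little and in the conservative direction.

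**The case against.** - **A coherent reading exists.** The zero sentence could be for patients with nothing after baseline, and the missing sentence for those with some later value who miss visit 10 or 11. Alternatively, each sentence could belong to a different analysis. Either reading would remove the conflict, but neither is written, so the sponsor would still have to state it.
- **The trigger is narrower than a missed follow-up.** Any measurement at a later treatment visit counts as post-baseline. A Group B subject never measured later may also lack a baseline. Both facts push the zero-filled share below the share who skip follow-up. This stands: unequal shares are plausible because follow-up is optional only in Group B, but they are not certain, and nothing in the documents supports 50% or 80%.
- **The large rates need strong assumptions.** The highest ones require those unsupported shares and a true change of one full SD. Equal true change is itself assumed, since treatment numbers and spacing may differ between groups. The formula is a better guide than the upper cells of the table.
- **Little depends on this comparison.** It is additional and non-randomised, and section 2.1 enrols Group B for training and experience only. Its p-value has limited meaning under either rule. This stands and limits the severity.
- **Choosing missing over zero is a judgement.** The contradiction alone requires only one stated rule. Leaving values missing also removes people whom section 2.15.3 counts as part of the study. That cost is real and should be stated.

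**Conclusion.** The concern holds. Section 2.15.5 gives two incompatible instructions for one value, section 2.15.3 does not resolve them, and the triggering variable is undefined.

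Under the zero rule with equal true change mu, the visit 11 comparison is biased by mu(fB - fA). The sign depends on which group has the larger share without post-baseline data. In the lower-range illustrations (shares of 10% to 20%, -2 cm, SD 2 cm), the false-positive rate runs from about 5% to 9%. Higher rates need shares that the documents do not support.

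The defect does not reach the primary safety conclusion or the success criteria in section 2.15.1. It should be fixed before analysis, but it does not threaten the study's main objective.

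**What to change.** **Needed to remove the contradiction**

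- In section 2.15.5, replace the reference to a primary efficacy variable with the named variable or variables, for example circumference.
- State one rule. The recommended one is to delete the zero-change assumption and leave visit 10 and 11 changes missing in the mixed model.
- In section 2.15.3, replace the open missing-value sentence with a reference to that rule.

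**Recommended alongside it**

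- State that the model assumes missingness is unrelated to the unobserved outcome, given the model.
- State that subjects with no value at visit 10 or 11 contribute nothing to the model, although section 2.15.3 counts everyone who begins treatment.
- Compute change only for subjects with a baseline value.
- Report by group the number with no baseline and the number with no post-baseline assessment.
- Keep zero imputation only as a labelled sensitivity analysis.

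**Cost:** a few lines of text and two counts per group, with no new data. The downside is that the main model leaves out subjects with no visit 10 or 11 value, and the zero-imputed result becomes supportive only.

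### Within-group significance of the change from baseline is taken from a paired t-test that, at Visit 11, drops subjects seen only at Visit 10, although a mixed model using their data is already planned

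*Combined protocol and SAP*

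**What the plan says.** Section 2.15.5 sets the time point: "Additional efficacy variable is the change from baseline to Visit 11 (90 day follow up visit"). It then plans a model: "The change from baseline to visits 10 and 11 will be analyzed using a Mixed Model Repeated Measures Analysis of Variance". The one stated use of that model is between groups: "A pairwise treatment group comparison at visit 11 will be performed using the results of this analysis". The two-sided 0.05 threshold is attached to that comparison ("Statistical significance with respect to the treatment group comparison at visit 11 will be declared if the two-sided p-value is" below 0.05).

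Within-group change is handled separately, at the end of the section: "The statistical significance of the mean change from baseline for each treatment group will be determined using a paired t-test". This sentence names no visit and no significance level.

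Two sentences deal with missing values. A patient who "has no post-baseline assessment of the primary efficacy variable it will be assumed that the change from baseline to visit 11 is zero". The next sentence reads: "The changes to visits 10 and 11 will be left as missing". Section 2.15.3 leaves the general method for missing values to be chosen later.

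On populations, 2.15.3 says of the intention-to-treat approach: "Everyone who begins the treatment is part of the study whether he or she completes the study or not". Its second paragraph bases the efficacy analysis on randomized patients with at least one treatment. Section 2.1 rules out randomization, so I read this as all treated patients. Section 12.0 says that data gathered before a withdrawal will be used in the analysis.

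**The concern.** A subject with a Visit 10 value and no Visit 11 value has a post-baseline assessment, so the zero-change rule does not apply. No other imputation is specified. That subject has no Visit 11 pair and drops out of the t-test, while a likelihood-based mixed model would use the Visit 10 change. The plan would then hold two different estimates of the same Visit 11 mean and attach the within-group p-value to the one that uses less of the data. This sits poorly with basing efficacy on all treated patients and with using data collected before withdrawal.

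The within-group result carries weight because the group comparison says little about efficacy. Under 2.1 Group B is enrolled for training and experience, assignment is not random, and Group B follow-up is optional. For circumference, ultrasound and strength, the Group A change from baseline is the more informative result. If attendance at day 90 depends on the day 30 result, its estimate and p-value are distorted.

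**Working it through.** **No figure in the plan to reproduce.** Section 2.15.2 gives a total of 20 subjects with no effect size, SD, power or dropout rate. Sections 2.1 and 3.3 give 30, and the Group A share is not stated. Every input below is therefore an assumption.

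**Inputs.** n = 20 in the group; true change at Visit 11 of -1.50 (negative is favourable); SD of change 2.0; correlation ρ between the Visit 10 and Visit 11 changes of 0.6 or 0.8; normal data. Only subjects in the poorer half at Visit 10 miss Visit 11, each with probability p. With p = 0.3, 0.5 × 0.3 = 15% are missing (3 of 20); with p = 0.4, 20% (4 of 20).

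**Formula.** The mean of a half-normal variable is √(2/π) = 0.798. Completers have weight 0.5 from the better half and 0.5(1 - p) from the poorer half. Their mean Visit 10 change is therefore shifted in the favourable direction by 0.798 × p/(2 - p) SD. The shift carries to Visit 11 multiplied by ρ:

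bias = ρ × SD × 0.798 × p/(2 - p)

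| p | missing | ρ | bias | t-test mean | overstatement |
|---|---|---|---|---|---|
| 0.3 | 15% | 0.6 | 0.6 × 2.0 × 0.1408 = 0.169 | -1.669 | 11% |
| 0.3 | 15% | 0.8 | 0.8 × 2.0 × 0.1408 = 0.225 | -1.725 | 15% |
| 0.4 | 20% | 0.6 | 0.6 × 2.0 × 0.1995 = 0.239 | -1.739 | 16% |
| 0.4 | 20% | 0.8 | 0.8 × 2.0 × 0.1995 = 0.319 | -1.819 | 21% |

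Simulation of 8,000 trials per setting gave -1.668, -1.737, -1.744 and -1.818, all within 0.012 of these values.

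**The mixed model.** With two visits and monotone missingness, its Visit 11 mean is the completers' Visit 11 mean + b × (Visit 10 mean of all subjects - Visit 10 mean of completers), where b is the slope of Visit 11 on Visit 10. Selection on Visit 10 does not alter that slope, so the correction removes the bias shown. The simulated estimates at 15% missing were -1.500 and -1.511.

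**Other patterns.** If absence is unrelated to response, the bias is zero. If all absent subjects come from the better half, the signs reverse by symmetry: the t-test mean runs from -1.50 + 0.169 = -1.331 to -1.50 + 0.319 = -1.181, that is 11% to 21% too small.

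**Against sampling error.** With 17 completers the standard error is about 2.0/√17 = 0.485, and with 16 it is 2.0/√16 = 0.50. The bias is thus about one third (0.169/0.485 = 0.35) to two thirds (0.319/0.50 = 0.64) of a standard error.

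**Error rate.** A second simulation (6,000 runs per scenario) used n = 20, zero true change, ρ = 0.7, and poorer Visit 10 responders likelier, but not certain, to be the ones absent. At 10%, 20% and 30% missing, the t-test wrongly favoured the device in 6.7%, 10.7% and 15.4% of trials, against a nominal 2.5%. The model-based test gave 2.3% to 3.3%. With absence unrelated to response, the t-test gave 2.2% to 2.8%.

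**The zero-change rule.** If it is applied, it pulls the other way. One subject in 20 entered as zero turns a mean of -1.50 among the other 19 into -1.50 × 19/20 = -1.425.

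**The case against.** The strongest reply is that little hangs on this t-test. The success criteria in 2.15.1 do not use it: they rest on the side-effect profile and pain score, photographic identification, GAIS against a score of 4, and collected questionnaires. The only declared threshold in 2.15.5 belongs to the model-based group comparison. The primary objective is safety, and these measures are listed in 1.2 as optional. All of this stands. A reader might infer that the paired t-test decides whether the device works, or that it is the only evidence of change under the device. Neither follows, since GAIS and the blinded photographs also address change.

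A reader might also see a direct breach of intention-to-treat. That is too strong: 2.15.3 applies the term to the primary analysis, which concerns safety. What remains is the tension with its second paragraph and with 12.0.

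The t-test sentence names no visit, and a Visit 10 test would keep these subjects. But the same section defines the variable at Visit 11. The open clause in 2.15.3 could allow imputation, yet it specifies none for this case.

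Finally, the direction is assumed. Nothing in the documents says that poor responders skip day 90. The one named cause of missed follow-up is COVID-19, with a recall visit within a year, and withdrawing subjects are asked to attend a final visit. The scenario that confines absence to the poorer half is also a severe one, and because it makes absence depend on Visit 10 alone it favours the model by construction. These points limit the size of the problem. They do not make the t-test the better choice.

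**Conclusion.** The point holds as a choice of method. For the within-group change at Visit 11, the plan uses a test that discards subjects whose data its own model would use. The resulting bias can go either way: about 11% to 21% too large if the 15% to 20% absent all come from the poorer half at Visit 10, the same amount too small if all come from the better half, and none if absence is unrelated to response. These figures rest wholly on the assumed n, SD, effect, correlation and missingness. A reader might infer that the plan will overstate the effect; the documents support only that it could. The consequence is confined to the additional efficacy assessments.

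The conflict between the zero-change sentence and the left-as-missing sentence needs no assumption. For a subject with no post-baseline assessment, the two give different instructions.

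**What to change.** In 2.15.5:

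- Take the Group A mean change at Visits 10 and 11, its 95% CI and two-sided p-value from the planned mixed model, with visit as a factor and unstructured covariance. Fit it to Group A alone, or to both groups with group-by-visit terms and group-specific covariance, so that Group B's optional follow-up does not influence the Group A estimate.
- State the significance level for this within-group test.
- Specify small-sample degrees of freedom, for example Kenward-Roger.
- Keep the paired t-test as a labelled observed-case sensitivity analysis, and name its visit.
- Reconcile the two sentences so that a subject with no post-baseline assessment is either counted as zero change or left missing, and say in which analysis.

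The cost is a few sentences; no extra subjects, visits or data are needed. If no Visit 11 value is missing, the Group A model reproduces the paired t-test, so nothing is lost. The remaining limit is that the model relies on absence being explained by the observed data. If absence depends on the unseen Visit 11 result itself, neither method corrects it.
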